11.1.2 Thrombotic Events

Physicians should perform all testing required to fully characterize arterial or venous thrombotic/vascular events. In the REGARD study, venous thrombotic events (VTEs) were more frequent on the placebo arm than on ramucirumab (all grade 7.0% versus 3.8%; and Grade 3 or greater 4.3% and 1.3%, respectively). Arterial thrombotic events (ATEs) occurred in patients treated with ramucirumab (1.7% all grade; 1.3% Grade 3 or greater) and in no patients treated with placebo. In RAINBOW, the overall incidence of all grade and Grade ≥ 3 VTEs and arterial thromboembolic events were low and similar in both treatment arms (ramucirumab plus paclitaxel vs. placebo plus paclitaxel: all grade VTEs [4.0% vs. 5.5%] and Grade 3 or greater VTEs [2.4% vs. 3.3%]; all grade ATEs [1.8% vs. 1.5%] and Grade 3 or greater ATEs [0.9% vs. 0.9%]).

Because therapy with antiangiogenic agents has been shown to be feasible in the setting of anticoagulation in patients with upper GI malignancies (12), patients who develop Grade 3 and 4 venous thrombotic events (deep vein thrombosis [DVT] or pulmonary embolism [PE]) may continue ramucirumab therapy if the event is not considered to be life-threatening in the opinion of the patient's physician, the patient is asymptomatic, and/or the event can be adequately treated with low molecular weight heparin-based therapy.

Patients with unresected primary tumors (or local recurrence) who develop Grade 3 and 4 venous thromboembolism may also receive anticoagulation and continue ramucirumab therapy (as detailed above), provided that the tumor does not confer an excessive bleeding risk, in the opinion of the patient's physician.

Grade 3 and 4 arterial thromboembolic events, or any PE/DVT occurring or worsening during anticoagulant therapy, require permanent discontinuation of ramucirumab therapy. Any venous

[Type here]

[Type here]

[Type here]

Pembrolizumab + Ramucirumab (Ver 2.5, Oct 2024)

or arterial event leading to discontinuation of ramucirumab therapy will be considered serious and should be reported via the SAE mechanism.

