	
For patients with only non-measurable disease from at baseline, categorization of objective tumor response assessment will be based on the modified RECIST 1.1 response criteria: CR, PD, non-CR/non-PD.
 
If the investigator is not sure whether progression has occurred, especially if there is a reaction to a non-target lesion (NTL) or a new lesion develops, if clinically necessary, dosing can be continued before next scheduled visit and be advisable to re-evaluate the patient's condition.
 
If progress is confirmed in the repeat scan, the progress date should be declared as the first scan date.
 
Secondary efficacy assessment will be conducted as follows:
 
 Best Overall Response Rate (BORR) is defined as the proportion of the patients who have achieved CR or PR at least once. Disease Control Rate (DCR) is defined as the proportion of the patients with a documented CR, PR, and SD (results will be provided by confirmed and unconfirmed). Progression-Free Survival (PFS) is defined as the time from first administration of investigational drug to the earlier date of PD or death due to any cause. Overall Survival (OS) is defined as the time from first administration of investigational drug to death due to any cause. Duration of Overall Response (DOR) is defined as the time from the first date of assessment as CR or PR to the earlier date of PD or death due to any cause. Maximal Tumor Shrinkage(MTS) is defined as rate of change in tumor size relative to the baseline at the time of best improvement. 
2. Safety assessment
 
The severity of all AEs will be graded for laboratory toxicity and symptoms according to NCI-CTCAE Ver. 5.0. For the events that are not pre-defined in terms under NCI-CTCAE, Investigator should assign a numeric grade of “1” to “5” using the definitions as Mild, Moderate, Severe, Life-threatening, Death, respectively based on maximal intensity.
 
3. Biomarker assessment
 
To collect and store diagnostic and/or archival tumour samples and any fresh tumour biopsies (pre-treatment if clinically feasible and before 3 cycles if clinically feasible) for potential future exploratory research into factors that may influence development and/or response to ramucirumab in combination with pembrolizumab. Next generation sequencing from these samples and/or other protein based exploratory analysis will be carried out. Fresh tissues at baseline is required if clinically feasible

--	---

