8.4 Special Treatment Considerations

8.4.1 Dose Adjustments and Delays

Ramucirumab

Dose modifications are permitted for ramucirumab in the setting of non-life-threatening, reversible Grade 3 and 4 AEs (that is, fatigue, anorexia, or fever) that resolve to Grade ≤ 1 within 1 treatment cycle (approximately 2 weeks). In this setting, ramucirumab may be readministered. If a second
[Type here] [Type here] [Type here]

Pembrolizumab + Ramucirumab (Ver 2.5, Oct 2024)

instance of such an event occurs, ramucirumab should be subsequently readministered at a dose of 6 mg/kg every other week. A second dose reduction to 5 mg/kg every other week is permitted for this level of event (Grade 3 and 4). If a Grade 4 AE occurs and is deemed at least possibly related to ramucirumab, then ramucirumab should be discontinued except in specific case of Grade 4 fever or Grade 4 laboratory abnormalities. If Grade 4 fever or laboratory abnormalities resolve to Grade ≤ 1 or pretreatment baseline within one treatment cycle (approximately 2 weeks), treatment with ramucirumab may be continued at the discretion of the treating physician. Criteria for dose reduction in the setting of hypertension or proteinuria and other AESIs are detailed in Section 11

Patients who enter the study with symptoms or laboratory values equivalent to NCI-CTCAE Version 4.03 Grade 1 to 2 AEs should not have dose reductions related to the persistence or mild worsening of those symptoms or laboratory values; dose reductions may be warranted if worsening of symptoms or laboratory values is clinically significant in the opinion of the patient's physician. Asymptomatic Grade 3 to 4 laboratory abnormalities should not result in dose interruptions, modifications, or discontinuation of protocol therapy unless determined to be clinically significant by the patient's physician (or unless otherwise specified in this protocol).

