Appendix 2 (Cyramza Safety Language)

The following items MUST be included in the appropriate Inclusion/Exclusion Criteria/Discontinuation sections as well as in the text of the appropriate or corresponding section of the protocol:

Hematologic Function

To be included in a ramucirumab clinical trial:

The patient has adequate hematologic function, as evidenced by an absolute neutrophil count (ANC) $\geq 1500/\mu\text{L}$, hemoglobin ≥ 9 g/dL (5.58 mmol/L), and platelets $\geq 100,000/\mu\text{L}$.

Coagulation:

The patient has adequate coagulation function as defined by International Normalized Ratio (INR) ≤ 1.5 and a partial thromboplastin time (PTT) (PTT/aPTT) $< 1.5 \times$ upper limits of normal [ULN]. Patients on full-dose anticoagulation must be on a stable dose (minimum duration 14 days) of oral anticoagulant or low molecular weight heparin (LMWH). If receiving warfarin, the patient must have an INR ≤ 3.0 . For heparin and LMWH there should be no active bleeding (that is, no bleeding within 14 days prior to first dose of protocol therapy) or pathological condition present that carries a high risk of bleeding (for example, tumor involving major vessels or known varices).

For Ramucirumab combined with Chemotherapy studies:

Coagulation: The patient must have adequate coagulation function as defined by International Normalized Ratio (INR) ≤ 1.5 , and a partial thromboplastin time (PTT) ≤ 5 seconds above the ULN (unless receiving anticoagulation therapy). Patients receiving warfarin must be switched to low molecular weight heparin and have achieved stable coagulation profile prior to first dose of protocol therapy.

To be excluded from a ramucirumab clinical trial:

The patient has experienced any Grade 3-4 GI bleeding within 3 months prior to first dose of protocol therapy.

The patient has a history of deep vein thrombosis (DVT), pulmonary embolism (PE), or any other significant thromboembolism (venous port or catheter thrombosis or superficial venous thrombosis are not considered “significant”) during the 3 months prior to first dose of protocol therapy.

Discontinuation of patient from a ramucirumab clinical trial:

Patients with unresected primary tumors (or local recurrence) who develop Grade 3 and 4 venous thromboembolism may also receive anticoagulation and continue ramucirumab therapy provided that the tumor does not confer an excessive bleeding risk, in the opinion of the patient’s physician.

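### Section 8.4.1 stops ramucirumab for a related Grade 4 event other than fever or laboratory values, while Sections 11.1.2 and 9.1 and Appendix 2 permit it to continue after venous thromboembolism, including Grade 4

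*Combined protocol and SAP*

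**What the plan says.** Four places in the protocol bear on a venous thrombotic event during treatment.

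- **Section 8.4.1 (Dose Adjustments and Delays, Ramucirumab).** The trigger is "If a Grade 4 AE occurs and is deemed at least possibly related to ramucirumab"; the action is "then ramucirumab should be discontinued except in specific case of Grade 4 fever or Grade 4 laboratory abnormalities". The same paragraph ends with a pointer: "Criteria for dose reduction in the setting of hypertension or proteinuria and other AESIs are detailed in Section 11".
- **Section 11.1.2 (Thrombotic Events).** For PE (pulmonary embolism) or DVT (deep vein thrombosis) of Grade 3 or 4, the wording is that patients "may continue ramucirumab therapy if the event is not considered to be life-threatening in the opinion of" their doctor. Two further conditions follow: that the patient has no symptoms, and/or that low molecular weight heparin (LMWH) can treat the event adequately. Relatedness to ramucirumab is not mentioned.
- **Section 9.1 (Concomitant Therapy, Ramucirumab).** A patient who develops venous thromboembolism (VTE) on protocol therapy may stay on study therapy but must receive LMWH. There is no limit by grade or relatedness.
- **Appendix 2 (Coagulation, discontinuation rules).** Patients with an unresected primary tumor or local recurrence "who develop Grade 3 and 4 venous thromboembolism may also receive anticoagulation and continue ramucirumab therapy", provided the physician does not consider the bleeding risk from the tumor excessive.

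Venous thrombotic events are listed among the adverse events of special interest (AESIs) in Section 10.2.5.

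**The concern.** A patient with a Grade 4 PE judged possibly related to ramucirumab falls under both sets of text. Section 8.4.1 says the drug should be discontinued, and thrombosis is not among its exceptions. Sections 11.1.2 and 9.1, and Appendix 2 for some patients, say the drug may continue. Two investigators, or one investigator with two patients, could act differently and each cite the protocol.

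This matters for patient safety first. It also affects the recorded data. Drug exposure and the reason for discontinuation would depend on which section was read. Section 11.1.2 makes a thrombotic event that leads to discontinuation of ramucirumab serious and reportable as a serious adverse event (SAE), so the choice can also change reporting. The effect may reach pembrolizumab: Section 7.1 says it stops when ramucirumab stops, whereas the Synopsis says it continues if ramucirumab is stopped for intolerable toxicity.

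**Working it through.** The point is textual, and the plan states no figure to reproduce. The check sets the rules side by side and then asks how often the case could arise.

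**1. Do the rules cover the same event?**

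| Place | Grade | Relatedness | Instruction |
|---|---|---|---|
| 8.4.1 | 4 | at least possibly related | should be discontinued, except fever and laboratory abnormalities |
| 11.1.2 | 3 and 4 DVT/PE | not mentioned | may continue, under conditions |
| 9.1 | any VTE | not mentioned | may continue, on LMWH |
| Appendix 2 | 3 and 4 VTE, unresected primary or local recurrence | not mentioned | may continue, subject to bleeding risk |

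The overlap is a Grade 4 DVT or PE that is at least possibly related. An unrelated Grade 4 event does not trigger 8.4.1, so there is no conflict for it.

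**2. Is the overlap more than nominal?** Section 10.2.2 counts probably related, possibly related and unknown causality all as related, and reserves the unrelated category for events that are without question not due to treatment. The related category is therefore broad.

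**3. Does the pointer to Section 11 resolve it?** It is worded for dose-reduction criteria only. Section 8.4.1 does have an override for rules specified elsewhere in the protocol, but attaches it to asymptomatic laboratory abnormalities, not to the Grade 4 rule. The specific rules naming Grade 4 infusion reactions (10.2.6), hypertension (11.1.1), arterial events (11.1.2) and bleeding (11.1.3) all stop ramucirumab, in line with 8.4.1. Venous events differ, and 8.4.1 does not list them.

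**4. What does the and/or in 11.1.2 mean?**
- Read as *and*: the event must be judged not life-threatening, alongside the other conditions. That sits poorly with Grade 4 where the protocol describes that grade: the Synopsis scale ("using the definitions as Mild, Moderate, Severe, Life-threatening, Death, respectively based on maximal intensity"), infusion reactions in 10.2.6 and hypertension in 11.1.1.
- Read as *or*: treatability with LMWH alone could be enough, the judgement on threat to life need not be met, and the conflict with 8.4.1 is wider.

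Section 11.1.2 carries its conditions over to unresected primaries by cross-reference. The parallel sentence in Appendix 2 lacks that cross-reference, so those conditions drop out there.

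**5. How often could it arise?** Inputs: 26 patients (Section 12), and the Grade 3 or worse VTE rates on ramucirumab in Section 11.1.2, 1.3% (REGARD) and 2.4% (RAINBOW, with paclitaxel).
- Expected events, n × p: 26 × 0.013 = 0.34; 26 × 0.024 = 0.62.
- Chance of at least one, 1 − (1 − p)^n: 1 − 0.987^26 = 28.8%; 1 − 0.976^26 = 46.8%.

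These count all Grade 3 or worse events, related or not. The conflict concerns only the related Grade 4 subset, whose share the documents do not give.

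**The case against.** The strongest reply is that the specific section governs the general one. Section 8.4.1 sets a default, Section 11 deals with adverse events and dose modification by type, and 8.4.1 points there for AESIs. That is a reasonable reading, but the protocol does not state it, and the pointer is limited to dose reduction.

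Second, Section 11.1.2 only permits continuation. A physician who stops for a related Grade 4 VTE complies with every section, so the documents do not force continued dosing. This stands and narrows the point: the conflict is between a stop instruction and a permission to continue. A physician who uses the permission still departs from 8.4.1.

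Third, Section 11.1.2 reports fewer VTEs on ramucirumab than on the comparator (all grades 3.8% versus 7.0%, and 4.0% versus 5.5%), so some events may be judged unrelated. That also stands, although the broad definition in Section 10.2.2 limits it.

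A reader might infer more: that a Grade 4 event is by definition life-threatening, so a Grade 4 VTE could never meet the first condition in 11.1.2. The documents do not support this. The Synopsis scale applies only to events that NCI-CTCAE does not pre-define, and the wording in 10.2.6 and 11.1.1 is specific to infusion reactions and hypertension. No section defines Grade 4 for venous thrombosis. Section 8.4.1 itself speaks of "non-life-threatening, reversible Grade 3 and 4 AEs (that is, fatigue, anorexia, or fever", so it recognises Grade 4 events that do not threaten life. The and/or may also make the condition optional. Moreover, if the condition were mandatory and Grade 4 always life-threatening, 11.1.2 would never permit continuation after Grade 4 and would not conflict with 8.4.1 at all. The two arguments cannot both be pressed in full.

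**Conclusion.** The conflict holds for one defined case: a Grade 4 DVT or PE at least possibly related to ramucirumab. Section 8.4.1 says to discontinue; Sections 11.1.2 and 9.1, and Appendix 2 where the primary is unresected or has recurred locally, permit continuation; no stated order of precedence settles it. Separately, the and/or in 11.1.2 leaves the conditions for continuing undefined. The tension between Grade 4 and not life-threatening is a reason to clarify the wording, not a proven contradiction.

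The frequency is unknown. A reader might take 29% to 47% as the chance of meeting this conflict; it is only a loose upper bound. It assumes that the cited trial rates carry over to this regimen and that 26 patients are treated. It includes Grade 3 and unrelated events, and its upper end comes from ramucirumab plus paclitaxel. No effect on the response-rate analysis, type I error or power is claimed. The change should be made because it concerns a safety stopping rule and is cheap.

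**What to change.** Reconcile Sections 8.4.1, 9.1 and 11.1.2 and Appendix 2 so that one rule applies to related Grade 4 venous events. Either state which section takes precedence or, if continuation is intended, list the exception in 8.4.1. In 11.1.2, replace and/or with explicit logic showing which conditions must all hold and which are alternatives, and say how the judgement on threat to life applies to a Grade 4 venous event. Make 9.1 and Appendix 2 refer to that single rule, including any limit by grade or relatedness. Which rule is adopted is for the clinical team. The cost is amendment wording only, with no change to sample size or analysis.

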11.1.3 Bleeding (Hemorrhagic) Events

Serious hemorrhagic AEs have been reported from clinical studies investigating ramucirumab. Hemorrhagic complications are associated with some malignancies (ie, variceal bleeding from portal hypertension in hepatocellular carcinoma, lower GI hemorrhage from bowel metastases in ovarian carcinoma), although the rate of these complications varies considerably. As detailed in the IB, the incidences of hemorrhagic events to date, significant background incidence of bleeding in some malignancies, and use of concomitant antiplatelet therapy in some of the reported cases precludes any definitive association between bleeding and ramucirumab, although ongoing surveillance and identification (and exclusion) of patients with high bleeding risk remain essential.

Ramucirumab therapy should be discontinued in the event of any Grade 3 or 4 bleeding (hemorrhagic) event.

11.1.4 Proteinuria

If, while on therapy, a patient has proteinuria $\geq 2+$ per a dipstick or routine UA, a 24-hour urine collection should be conducted. If the protein level is 2g to 3g/24 hours, protocol therapy will be temporarily discontinued for up to 2 weeks and a 24-hour urine collection will be repeated. Ramucirumab will resume at a reduced dose level (6 mg/kg every other week) once the protein level returns to < 2 g/24 hours. A second dose reduction (to 5 mg/kg every other week) is permitted if the protein level > 2 g/24 hours recurs. The patient will have ramucirumab permanently discontinued if the protein level is > 3 g/24 hours, if there is a third occurrence of > 2 g/24 hours, or if the protein level does not return to < 2 g/24 hours within 2 weeks.

11.1.5 Gastrointestinal Perforation

Patients with unresected (or recurrent) primary tumors, mesenteric or peritoneal disease who participate in this clinical trial may be at increased risk for gastrointestinal perforation and/or fistula due to the nature of their metastatic gastric cancer. All cases of perforation and fistula should be reported via the SAE mechanism.

Ramucirumab should be permanently discontinued in the event of a gastrointestinal perforation.

11.1.6 Reversible Posterior Leukoencephalopathy Syndrome (RPLS)

Reversible posterior leukoencephalopathy syndrome is a clinical and radiologic syndrome
[Type here] [Type here] [Type here]

Pembrolizumab + Ramucirumab (Ver 2.5, Oct 2024)

typically consisting of reversible cortical neurological dysfunction and brain-imaging findings of subcortical edema involving the posterior circulation, particularly the occipital lobes (51). The symptoms of RPLS most often include generalized seizures, headache, delirium, and cortical blindness, although these may vary significantly and occasionally include focal neurological deficits (50,52,53). Magnetic resonance imaging represents the most reliable method for the diagnosis (52). Clinical symptoms and MRI abnormalities usually recover within days to weeks with proper management, although permanent neurologic dysfunction has been reported (50,51,52,54).

Reversible posterior leukoencephalopathy syndrome has been associated with multiple clinical conditions including hypertensive encephalopathy, eclampsia, and renal failure with hypertension as well as the use of both immunosuppressive and cytotoxic drugs (51,55). Reversible posterior leukoencephalopathy syndrome has been associated with the use of the anti- VEGF agent bevacizumab, as described in the prescribing information for this agent (54,56).

While the precise pathogenesis of RPLS has not been established, the pathophysiology may involve impaired cerebrovascular autoregulation leading to blood-brain barrier disruption and vasogenic edema (57). Although the pathogenesis of RPLS appears to be multifactorial, drug-induced endothelial damage and acute hypertension are frequently proposed causes of cerebrovascular dysfunction in RPLS (54).

Reversible posterior leukoencephalopathy syndrome should be identified and treated promptly in order to minimize potential for permanent neurological damage. Treatment encompasses careful control of BP, withdrawal of potentially causative medication, and administration of anticonvulsant agents to those experiencing seizures (56).

One SAE of RPLS has been reported in the double-blind, randomized, placebo-controlled Phase 3 colorectal cancer study CP12-0920 (I4T-MC-JVBB). The event was determined to be related to administration of all study drugs, including blinded investigational drug product. (The treatment assignment for this patient remains blinded.) Because hypertension is an identified risk for ramucirumab, physicians should control BP in accordance with established guidelines.

In addition, physicians should consider a diagnosis of RPLS in the setting of seizures, headache, nausea, delirium, visual changes, and/or other unexplained neurological symptoms, especially in combination with hypertension and MRI findings of hyperintensity on T2-weighted and fluid-attenuated inversion recovery images.

No cases of RPLS have been specifically associated with ramucirumab therapy to this time. If the diagnosis of RPLS is confirmed, ramucirumab must be permanently discontinued. All cases of RPLS must be reported via the SAE mechanism.

An increased risk of CHF has been associated with some antiangiogenic therapeutic agents, particularly in patients with metastatic breast cancer previously/concomitantly treated with anthracyclines or with other risk factors for CHF, including prior radiotherapy to the left chest wall. Findings have ranged from asymptomatic declines in left ventricular (LV) ejection fraction to symptomatic CHF requiring treatment or hospitalization. Caution should be exercised when treating patients with clinically significant cardiovascular disease such as preexisting coronary artery disease or CHF. Patients with symptomatic CHF, unstable angina pectoris, or symptomatic or poorly controlled cardiac arrhythmia should not be enrolled in clinical trials with ramucirumab.

